APPENDIX A. WALKING IMPAIRMENT QUESTIONNAIRE (WIQ)

1. WALKING IMPAIRMENT: These questions ask about the reasons why you had difficulty walking. We would like to know how much difficulty you had walking during the last week. By difficulty, we mean how hard it was or how much physical effort it took to walk because of each of these problems.

A. PAD SPECIFIC QUESTIONS	LEG	DEGREE OF DIFFICULTY				
		None	Slight	Some	Much	Very
1. Pain, aching, or cramps in your calves? (or buttocks)	Right	4	3	2	1	0
	Left	4	3	2	1	0
	Both	4	3	2	1	0

B. DIFFERENTIAL DIAGNOSIS	DEGREE OF DIFFICULTY				
	None	Slight	Some	Much	Very
1. Pain, stiffness, or aching in your joints (ankles, knees, or hips)?	4	3	2	1	0
2. Weakness in one or both of your legs?	4	3	2	1	0
3. Pain or discomfort in your chest?	4	3	2	1	0
4. Shortness of breath?	4	3	2	1	0
5. Heart Palpitations?	4	3	2	1	0
6. Other Problems? (Please list)					
a.	4	3	2	1	0
b.	4	3	2	1	0
c.	4	3	2	1	0

2. WALKING DISTANCE: Report the degree of physical difficulty that best describes how hard it was for you to walk on level ground without stopping to rest for each of the following distances during the last week:

DISTANCE	DEGREE OF DIFFICULTY				
	None	Slight	Some	Much	Very
1. Walking indoors such as around your home?	4	3	2	1	0
2. Walking 15 meters or 50 feet?	4	3	2	1	0
3. Walking 45 meters or 150 feet (1/2 block)?	4	3	2	1	0
4. Walking 90 meters or 300 feet (1 block)?	4	3	2	1	0
5. Walking 180 meters or 600 feet (2 blocks)?	4	3	2	1	0
6. Walking 270 meters or 900 feet (3 blocks)?	4	3	2	1	0
7. Walking 450 meters or 1500 feet (5 blocks)?	4	3	2	1	0

3. WALKING SPEED: Report the degree of physical difficulty that best describes how hard it was for you to walk one city block on level ground at each of these speeds without stopping to rest during the last week:

SPEED	DEGREE OF DIFFICULTY				
	None	Slight	Some	Much	Very
1. Walking 1 block slowly?	4	3	2	1	0
2. Walking 1 block at an average speed?	4	3	2	1	0
3. Walking 1 block quickly?	4	3	2	1	0
4. Running or jogging one block?	4	3	2	1	0

4. STAIR CLIMBING: Report the degree of physical difficulty that best describes how hard it was for you to climb stairs for each of these questions without stopping to rest during the past week:

STAIRS	DEGREE OF DIFFICULTY				
	None	Slight	Some	Much	Very
1. Climbing 1 flight of stairs	4	3	2	1	0
2. Climbing 2 flights of stairs	4	3	2	1	0
3. Climbing 3 flights of stairs	4	3	2	1	0

1. INTRODUCTION

Infrainguinal peripheral arterial occlusive disease (PAD) is manifest over a spectrum of clinical presentations, ranging from the asymptomatic loss of peripheral pulses, leg claudication, to pain at rest, gangrene and limb-loss. The magnitude of signs and symptoms is well correlated with the anatomic extent of disease. Single-level, short arterial obstructions with moderate levels of stenosis may remain asymptomatic, while multilevel, long-segment occlusions often culminate in ischemic complications that threaten the viability of the limb.

The Rex Medical Revolution™ peripheral Atherectomy System is intended for use in peripheral vessels of suitable patients with atherosclerotic PAD.

1.1 Design, Treatments and Visits

The Reveal study is a multi-center prospective, non-randomized, single arm study and will enroll up to 121 subjects with PAD and significant target lesions of the appropriate diameter, located within the superficial femoral artery (SFA), popliteal and tibial arteries.

Data will be collected at baseline (screening), index procedure, hospital discharge, 1-month post index procedure and 6-months post index procedure. And adverse events will be collected at the index procedure, hospital discharge and through 6 months. Rutherford category, ankle-brachial or toe-brachial index and duplex ultrasound (DUS) of the target vessel will be collected at 1 month and 6 months.

1.2 Objectives

The purpose is to evaluate the safety and effectiveness of the Revolution™ Peripheral Atherectomy System in the treatment of infrainguinal lower extremity peripheral arterial occlusive disease.

Safety will be evaluated by assessing freedom from 30-day Major Adverse Event (MAE), defined as the composite of all-cause mortality, clinical-drive target lesion revascularization (TLR), major target limb amputation, major target vessel perforation requiring surgical or endovascular repair and clinically-significant distal embolization in the target limb as adjudicated by the independent Clinical Events Committee (CEC).

Effectiveness will be evaluated by acute debulking, assessed by technical success ($\leq 50\%$ diameter stenosis) after atherectomy with the study device, prior to adjunctive therapy with balloon angioplasty, stent deployment or other interventions. Effectiveness will be evaluated from post-atherectomy contrast angiograms, as evaluated by the independent core laboratory. Effectiveness will be assessed for all investigator-identified target lesions and calculated as the proportion of investigator-identified target lesions with technical success.

1.3 Randomization

This is not a randomized study.

2. ENDPOINT DEFINITIONS

2.1 Primary Safety Endpoint

The primary safety endpoint is a composite endpoint triggered by the occurrence of any five categories of events through 30 days after the index procedure¹. These events are the following:

1. All-cause mortality- Death from any cause, from the point of enrollment through 30 days.
2. Clinically-driven TLR- Any revascularization of the target lesion that occurs after the subject has left the procedure room following the index procedure. TLR do not include adjunctive interventions performed during the index procedure, whether planned or for failed atherectomy or for complications of atherectomy. TLRs are considered to be clinically-driven when they occur as a result of restenosis >50% diameter reduction as measured angiographically or by duplex ultrasound (occlusion or stenosis with Peak Systolic Velocity Ratio >2.4)².
3. Perforation of the target vessel- Imaging evidence (standard contrast angiography, computed tomography angiography or open surgical/pathology visualization) of target vessel perforation from any cause. For angiography and CTA, perforation is defined by contrast extravasation outside of the adventitia.
4. Clinically- significant distal embolization- Target limb embolization documented on core laboratory- assessed angiography or with open surgery/pathology, accompanied by symptoms referable to the involved vascular bed.
5. Major amputation- Amputation of the target limb that results in limb shortening; i.e. is performed at or above the level of the malleoli.

The composite endpoint and each individual component are all subject level endpoints.

¹ The index procedure is considered to occur on day 0; the first post-procedure day is day 1, and so on. The 30-day time point includes any events with a start date prior to 11:59PM on day 30.

² If an angiogram and a duplex ultrasound imaging study are discordant within any 30-day period, the angiographic results will supersede the duplex findings.

2.2 Primary Effectiveness Endpoint

The primary effectiveness endpoint is technical success defined as acute debulking resulting in a reduction of stenosis to $\leq 50\%$ after treatment with RevolutionTM Peripheral Atherectomy System from baseline and prior to other adjunctive therapies at the conclusion of the index procedure, as measured by angiographic core laboratory.

Within any target lesion, stenosis is measured at the point of the minimum luminal diameter (MLD) over its shoulder -to – shoulder length³. The reference vessel diameter (RVD) is the interpolated diameter from the point just proximal to the point just distal to the target lesion. The percent stenosis is calculated as:

$$\% \text{ Diameter Stenosis} = 1 - \text{MLD}/\text{RVD}.$$

This is a lesion level endpoint.

2.1 Secondary Endpoints

Secondary endpoints will consist of the following with level of analysis in parentheses:

- 1) Change in percent stenosis after treatment with RevolutionTM Peripheral Atherectomy System, determined after atherectomy and prior to other adjunctive therapies, as measured by the angiographic core laboratory (lesion level);
- 2) Procedural success as defined by target lesion residual stenosis of $<30\%$ at the conclusion of the index procedure, after atherectomy and any adjunctive endovascular treatment, as measured by the angiographic core laboratory (lesion level);
- 3) Assessment of the individual components of the primary safety endpoint (MAE); including all-cause mortality, major target limb amputation, clinically significant distal embolization, major target vessel perforation requiring surgical or endovascular repair, and clinically-driven TLR, measure through 30 days and at 6 months (subject level);
- 4) Minor unplanned target limb amputation rate through 30 days and 6 months (subject level);
- 5) Myocardial infarction through 30 days and 6 months (subject level);

³ The shoulder-to-shoulder length is determined visually using a Quantitative Vascular Angiography (QVA) software application. RVD is determined at the location of the MLD, linearly interpolated between the luminal diameters just proximal to and distal to each shoulder.

- 6) Incidence of target vessel revascularization (TVR) through 30 days and 6 months (subject level);
- 7) Frequency of angiographic procedural distal embolization (symptomatic) in the target limb as confirmed angiographically by the core laboratory (subject level);
- 8) Primary patency of the target lesion at 30 days and 6 months, determined by duplex ultrasound or angiography (subject level);
- 9) Primary-assisted patency of the target lesion at 30 days and 6 months, determined by duplex ultrasound or angiography (subject level);
- 10) Secondary patency of the target lesion at 30 days and 6 months, determined by duplex ultrasound or angiography (subject level).

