5. OUTCOME VARIABLES

5.1. Primary Safety Endpoint Definition

The primary safety endpoint is a composite endpoint triggered by the occurrence of any of five categories of events through 30 days after the index procedure.^b These events are the following:

1. All-cause mortality- Death from any cause, from the point of enrollment through 30 days.
2. Clinically-driven TLR- Any revascularization of the target lesion that occurs after the subject has left the procedure room following the index procedure. TLR do not include adjunctive interventions performed during the index procedure, whether planned or for failed atherectomy or for complications of atherectomy. TLR are considered to be clinically-driven when they occur as a

^b The index procedure is considered to occur on day 0; the first post-procedure day is day 1, and so on. The 30-day time point includes any events with a start date prior to 11:59PM on day 30.

result of restenosis >50% diameter reduction as measured angiographically or by duplex ultrasound (occlusion or stenosis with Peak Systolic Velocity Ratio >2.4).^c

3. Perforation of the target vessel- Imaging evidence (standard contrast angiography, computed tomography angiography or open surgical/pathology visualization) of target vessel perforation from any cause. For angiography and CTA, perforation is defined by contrast extravasation outside of the adventitia.
4. Clinically-significant distal embolization- Target limb embolization documented on core laboratory-assessed angiography or with open surgery/pathology, accompanied by symptoms referable to the involved vascular bed.
5. Major amputation- Amputation of the target limb that results in limb shortening; i.e. is performed at or above the level of the malleoli.

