7.5. Secondary Endpoints

The following secondary endpoints will be studied:

1. Change in percent stenosis after treatment with Revolution™ Peripheral Atherectomy System, determined after atherectomy and prior to other adjunctive therapies, as measured by the angiographic core laboratory
2. Procedural success as defined by target lesion residual stenosis of $< 30\%$ at the conclusion of the index procedure, after atherectomy and any adjunctive endovascular treatment, as measured by the angiographic core laboratory;
3. Assessment of the individual components of the primary safety endpoint (MAE); including all-cause mortality, major target limb amputation, clinically significant distal embolization, major target vessel perforation requiring surgical or endovascular repair, and clinically-driven TLR, measured through 30 days and at 6 months.;
4. Minor unplanned target limb amputation rate through 30 days and 6 months;
5. Myocardial infarction through 30 days and 6 months;
6. Incidence of TVR through 30 days and 6 months;

^g Technical success is defined on the post-atherectomy angiogram, prior to adjunctive therapy with balloon angioplasty, stent deployment, or any other intervention.

^h Shan, G. C. Ma. Efficient tests for one sample correlated binary data with applications. *Stat Methods Appl*, 23:175-188, 2014.

7. Frequency of angiographic procedural distal embolization (symptomatic) in the target limb as confirmed angiographically by the core laboratory;
8. Primary patency of the target lesion at 30 days and 6 months, determined by duplex ultrasound or angiography;
9. Primary-assisted patency of the target lesion at 30 days and 6 months, determined by duplex ultrasound or angiography.
10. Secondary patency of the target lesion at 30 days and 6 months, determined by duplex ultrasound or angiography.

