An MAE is a subcategory of adverse events that include any of the primary safety endpoints occurring within 30 days of the index procedure. An adverse device effect (ADE) is any unwanted and unintended response to a medical device. This definition includes any event resulting from insufficiencies or inadequacies in the instructions for use or the deployment of the device and any event that is a result of user error. A serious adverse device effect (SADE) is an adverse device effect that has resulted in any of the consequences characteristic of a serious adverse event or that might have led to any of the consequences if suitable action had not been taken or intervention had not been made or if circumstances had been less opportune. An unanticipated adverse device effect (UADE) is defined as “any serious adverse effect on health or safety or any life-threatening problem or death caused by, or associated with, a device, if that effect, problem, or death was not previously identified in nature, severity, or degree of incidence in the investigational plan or application (including a supplementary

application), or any other unanticipated serious problem associated with the device that relates to the rights, safety, or welfare of subjects.”

Section 15.1 (page 44, below) includes a list of possible adverse events associated with endovascular repair, including those events considered major device-related events and major morbidity. These events are considered reportable at all time points throughout the trial and require submission to the Sponsor.

Events not captured in these two categories are not considered in the primary effectiveness or primary safety analyses, regardless if they are device-related or serious. These events must nonetheless be documented on the Adverse Event CRFs. Additionally, any event with an outcome of death must be reported.

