10.2. Reporting of Adverse Events

In addition to events considered in the primary effectiveness and primary safety analyses, all device- and/or procedure-related adverse events, as well as events resulting in death, must be captured on the Adverse Event Case Report Form. The report should include, wherever possible, severity, duration, outcome, and the Investigator’s written medical judgment as to the relationship of the adverse event to the study device, procedure, or underlying disease (i.e., not related, possibly related, definitely related, or relationship unknown).

All SAEs must be reported to the Sponsor or its Contract Research Organization (CRO) within 5 business days of the Investigator’s knowledge of the event. The event is reported in the electronic data capture system. IRB notification of the adverse event may also be required, depending on the conditions of approval or requirements of the respective committee. Any unanticipated adverse device effects must be reported to the Sponsor/CRO within 1 working day from when the Investigator first learns of it.

Non-serious reportable adverse events are to be submitted via the electronic data capture system in a timely fashion. Certain reportable events may require adjudication; therefore, supporting documentation must be sent to the Sponsor/CRO.

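### Secondary endpoint 7 is limited to symptomatic emboli, so an asymptomatic procedural embolus confirmed by the core laboratory is not explicitly counted in any prespecified endpoint

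*SAP*

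**What the plan says.** Endpoint 7 carries the same restriction wherever it is listed: the Protocol synopsis, Protocol section 4, Protocol section 7.5 ("Frequency of angiographic procedural distal embolization (symptomatic) in the target limb as confirmed angiographically by the core laboratory") and SAP section 2.1 Secondary Endpoints, where it reads "Frequency of angiographic procedural distal embolization (symptomatic) in the target limb as confirmed angiographically by the core laboratory (subject level"). The SAP adds only that it is analysed by subject.

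The embolization component of the 30-day MAE composite is item 4 in Protocol section 5.1 and in SAP section 2.1 Primary Safety Endpoint. It needs target-limb embolization shown on core-laboratory angiography, at open surgery or by pathology, and it must be "accompanied by symptoms referable to the involved vascular bed".

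Secondary endpoint 3 reports the MAE components individually, including "major target limb amputation, clinically significant distal embolization, major target vessel perforation requiring surgical or endovascular repair".

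On interventions during the index procedure, both documents state that "TLR do not include adjunctive interventions performed during the index procedure, whether planned or for failed atherectomy or for complications of atherectomy".

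Events outside the primary endpoint categories are still recorded. Protocol section 10.1 says "These events must nonetheless be documented on the Adverse Event CRFs", and section 10.2 says that "all device- and/or procedure-related adverse events, as well as events resulting in death, must be captured on the Adverse Event Case Report Form".

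**The concern.** The device ablates plaque and conveys the debris out through the catheter (Protocol section 2.8), and distal embolization is among the known risks in Protocol Table 7. The frequency of procedural emboli on angiograms read by the core laboratory is a direct measure of how well debris is captured. Endpoint 7 is the only secondary endpoint that appears designed to give that frequency, yet its qualifier removes the cases not already covered by the composite.

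At stake is the completeness of a secondary safety result. A reader of the final report could take endpoint 7 for the angiographic embolization rate when it is the symptomatic rate. An embolus that was seen, and perhaps treated, without causing symptoms would have no prespecified summary based on core-laboratory reading.

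**Working it through.** No arithmetic applies. The check has three steps.

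**Step 1. Look for any endpoint that counts the event.** Take an embolus in the target limb that arises during the procedure, is confirmed by the core laboratory, causes no symptoms, and may be treated before the subject leaves the room. There are five composite components and ten secondary endpoints.

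| Endpoint | Counts this embolus? | Reason |
|---|---|---|
| MAE 1, death | No | Different event |
| MAE 2, clinically-driven TLR | No | Starts after the subject leaves the procedure room; index-procedure interventions for complications are excluded |
| MAE 3, perforation | No | Different event |
| MAE 4, clinically significant embolization | No | Symptoms required |
| MAE 5, major amputation | No | Different event |
| Secondary 1 and 2, stenosis change and procedural success | No | Measure the target lesion, not the distal bed |
| Secondary 3, MAE components | No | Carries over the symptom condition of MAE 4 |
| Secondary 4 and 5, minor amputation and myocardial infarction | No | Different events |
| Secondary 6, TVR | Not explicitly | TVR is not defined in either document; the TLR exclusion suggests index-procedure treatment is out, and TVR would not identify an embolus anyway |
| Secondary 7, procedural embolization | No | Restricted to symptomatic cases |
| Secondary 8 to 10, patency | No | Target-lesion patency at 30 days and 6 months |

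None of the fifteen explicitly counts it.

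**Step 2. Compare endpoint 7 with MAE component 4.**

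| Feature | MAE component 4 | Secondary endpoint 7 |
|---|---|---|
| Site | Target limb | Target limb |
| Proof | Core-laboratory angiography, open surgery or pathology | Core-laboratory angiography |
| Time | Through 30 days | Procedural |
| Symptoms | Required | Required |

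Endpoint 7 is equal to or narrower than component 4 on every row. It is thus essentially a subset. *Essentially* is needed because component 4 asks for symptoms referable to the affected vascular bed and is adjudicated by the CEC, while endpoint 7 says only symptomatic and rests on core-laboratory confirmation. Endpoint 7 does isolate the procedural cases from those arising later within 30 days.

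**Step 3. Find where the event is recorded instead.**
- The Treatment CRF records additional procedures and adverse events (Protocol section 8.3).
- Device- or procedure-related adverse events go on the Adverse Event CRF (section 10.2).
- An event that needed intervention to prevent permanent impairment or damage is serious (section 10.1). It is then reported to the sponsor or CRO within 5 business days (section 10.2) and, if possibly or definitely related, adjudicated by the DSMB (section 13.5).
- SAP section 5.1 describes safety event rates by event term, so a rate from site-reported events is possible.

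The event is therefore recorded. What is missing is a prespecified frequency based on core-laboratory reading.

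**The case against.** The best defence is that the restriction is deliberate and surveillance is adequate. The synopsis, sections 4 and 7.2 of the Protocol and the SAP all qualify embolization in the composite as clinically significant. Events that need rescue can reach the sponsor, the DSMB and, under its charter, the CEC. All of that stands for the primary composite. It does not explain why the same restriction is repeated in an endpoint titled as angiographic and procedural, and neither document gives a reason.

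A reader might infer three stronger conclusions, which the documents do not support:

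- *Treatment on the table removes an embolus from the endpoints.* It does not. The dividing line is symptoms. A treated embolus with referable symptoms counts in component 4 and, if confirmed on angiography by the core laboratory, in endpoint 7. How symptoms are judged during a procedure is not stated; the CEC sets classification rules (Protocol section 13.4), but its charter is not among the documents.
- *Asymptomatic emboli would be invisible, or the trial could report almost no embolization whatever the angiograms showed.* Symptomatic confirmed emboli are counted, and the others should appear in adverse event and procedure data.
- *The MAE definition should be widened to include treated emboli.* That would change the primary endpoint while its 80% goal stayed fixed. The goal comes from 13 studies with a weighted MAE rate of 10.1% and a 10% margin (Protocol section 7.7), and the documents do not show how those studies counted emboli.

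One practical limit also stands. The supplied text does not say which distal views are required, and the Core Lab Manual is not included, so ascertainment of asymptomatic emboli may be incomplete.

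**Conclusion.** The point holds for asymptomatic procedural emboli and for the secondary endpoint only. As written, endpoint 7 largely repeats a component already reported under endpoint 3, and no listed endpoint explicitly counts an asymptomatic embolus confirmed by the core laboratory, whether or not it was treated during the procedure.

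The size cannot be put as a number, because neither document gives a rate for such emboli; all of them are omitted from endpoint 7. Nothing changes for the primary safety test, the 80% goal, the 110 evaluable and 121 enrolled subjects, or the planned power.

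The conclusion rests on the endpoint definitions in the two documents. It assumes that TVR, which is undefined, follows TLR in excluding interventions during the index procedure, and that no unseen charter or manual adds a separate embolization endpoint.

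**What to change.** In the Protocol synopsis, Protocol sections 4 and 7.5, and SAP section 2.1 Secondary Endpoints item 7, delete the parenthesised word *symptomatic*. The endpoint then counts every core-laboratory-confirmed procedural distal embolization in the target limb, by subject.

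Add to the SAP a descriptive table of these events by symptomatic or not, and by treated during the procedure or not. The count as now defined stays available as the symptomatic row.

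Leave the MAE composite, performance goal, sample size and power as they are.

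The cost is small. Endpoint 7 already depends on core-laboratory angiographic confirmation, and the Treatment CRF already captures additional procedures. The downside is that the reported embolization frequency may be less favourable.
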